## 9.2 Additional Safeguards:

Children are the targeted population for this study. Others that have been checked as “allowed” above are not being intentionally included or excluded. For example, we will not inquire about someone’s membership in a disenfranchised group, nor whether a target child’s parent is on active duty in the military. Our careful consent/assent procedures, designed to handle research with children, should be sufficient to cover other vulnerable participants who may inadvertently enter our study.

All of the subjects will be children, ranging 11-14 years old. This study focuses on adolescents because our goal is an analysis of the impact of social buffering and puberty on stress-mediating systems. Children have been the focus of our research for the past 30+ years. Our staff members are highly trained in working with children and families. The graduate students working on the project will be Child Psychology and/or Child Clinical Psychology Ph.D. students. The undergraduate research assistants will, for the most part, be majoring in child development.

Much of the work will be performed online over video conferencing. Staff will guide parents and children through the study procedures and participating families will likely be comfortable in their own homes.

Our laboratory has been scanning both typically developing children and adolescents (ages 4-17) and those at risk due to early health or environmental risks for over two decades. We have conducted NIH funded research with child participants at the CMRR for the past 16 years. We are very experienced in putting children at ease in the MRI scanner and ensuring that children are aware that they can stop at any time. We have completed a prior MRI study with 11- to 14-year-olds using the MISTiC social stress paradigm; therefore, we are confident that we are well positioned to properly inform children about the procedures and are not stressing children beyond normal everyday levels that they experience in school or in extracurricular activities (sports competitions; music, dance, or drama performances; etc.).

Parents provide consent, youth provide assent, and see below where that process is fully described to ensure that youth have full understanding and are free to decline participation.

## **10.0 Local Number of Participants**

*10.1 Local Number of Participants to be Consented:* We plan to analyze data from at least 200 target participants. To account for attrition between sessions/replacement for incomplete data, up to 300 children may be consented/enrolled.

## **11.0 Local Recruitment Methods**

*11.1 Recruitment Process:* Families will be initially contacted by phone, email, or paper mail to invite them to participate. Paper mail will include IRB-approved recruitment flyers. Interested families will be provided a more detailed overview of the study procedures in a telephone call. If the family is interested in participating, the parent will verbally complete a screening interview to assess inclusion and exclusion criteria, and for those who are eligible, the first visit will be scheduled. Copies of the consent and assent forms will be sent to families prior to the visit, along with directions to the University, and a reminder call will be a chance for families to confirm their interest in participation after having seen the consent forms. The formal consent process will occur at both of the two sessions.

*11.2 Identification of Potential Participants:* Potential participants will be identified using the ICD registries of families interested in being contacted about research. These families have agreed to be contacted, and once ICD Registry procedures have been followed, including proof of IRB approval,

an encrypted list is provided to study staff. No protected records are involved. Study staff will make initial contact.

*11.3 Recruitment Materials:* We will recruit via telephone, email, and paper mail (as parents have given us these three means of contacting them). We will also post flyers and put the flyer information on our website so that families can contact us. We will also email organizations what may be able to assist with sharing study contact information and spreading interest, using the Letter to Organizations template. We will also email organizations' listservs when approved to do so by the listserv administrators. Materials are uploaded in ETHOS.

*11.4 Payment:*

- Child Participant: \$40 debit or gift card for Visit 1; \$60 in debit or gift card for Visit 2
- Parent of Child Participant: \$25 in debit or gift card for Visit 1; \$25 in debit or gift card for Visit 2

Cards will be given at the session to parent & child as specified, though we will have parents sign receipts for payment. We intend to use Greenphire ClinCard prepaid debit cards for compensation and have included appropriate language in the consent document. We will provide a Target gift card instead of the ClinCard if parents object to the terms and conditions of the ClinCard.

## **12.0 Withdrawal of Participants**

*12.1 Withdrawal Circumstances:* If participants are enrolled (consent signed) and subsequently determined to meet exclusion criteria, their data will be excluded from analyses. Children may be withdrawn from the study without their consent if we discover a safety concern for MRI scanning after consent/assent. Children may also be withdrawn if the experimenter believes that the child is excessively distressed by the stress paradigm or MRI scanning procedures. Participants will receive full compensation for the session at which they are withdrawn.

*12.2 Withdrawal Procedures:* If participants voluntarily withdraw, we will verify permission to retain and use any data collected to that point. If participants wish to withdraw all permission, we will destroy any data collected from the participant but will keep their name in our study records with a note that they withdrew. This procedure prevents us from inadvertently enrolling participants more than once. If the participant is withdrawn by the researcher, we will retain and use any data collected from the participant.

*12.3 Termination Procedures:* Data will not be used after termination.

### 13.0 Risks to Participants

Foreseeable Risks: Puberty Staging: There is the risk of embarrassment. Both for the youth's well-being and to prevent study drop out, we are motivated to reduce any sense of embarrassment as much as possible in a study that requires the measurement of pubertal changes. The Morris and Udry questionnaire will be completed in privacy and in the comfort of the subject's home while connected via video conference.

Questionnaires: Youth or parents may experience concerns when completing questionnaires dealing with symptoms of behavior problems. Any time one works with youth there is the possibility that they will reveal information about abuse and/or indicate that they are thinking of hurting themselves or others. We are mandated reporters, a fact that is revealed in both consent and assent forms. However, in over a decade of working with children and youth drawn from our participant files, we have never encountered a reportable incident, so we consider this risk to be very low.

Minnesota Imaging Stress Test in Children: The MISTiC is a social evaluative stressor. Public speaking evokes anxiety in many individuals.

The MISTiC activates stress-mediating systems because it serves as a threat to the social self. Public speaking produces anxiety in most people. However, answering questions in class, speaking in front of the class or school, and solving problems in front of teachers and classmates is a common occurrence in children's lives. Thus, the MISTiC standardizes a common everyday stressor. To reduce risk, youth are told that they can stop without prejudice if they choose. Because they are told they are being evaluated (and this is a necessary part of the procedure), after the MISTiC session, the youth will be debriefed to make it clear that there were no judgements made about the speech or math performed. It will be explained that performance in a social evaluation task was used in order to elicit a physical stress response. The youth will never receive any negative evaluations from adults as part of being in this study. As a part of this debriefing, participants are told that they may withdraw their data and record of participation.

MRI Scanning: The primary risks associated with magnetic resonance scanning involve risk of injury or burn in the event that unsafe metallic objects are introduced into the scanner environment. Loose items have the potential to become projectiles while stationary metallic surfaces could build heat over time and cause a burn. In addition, implanted medical devices could become non-functional or experience torque that could move metal implants through body tissue. All participants are screened multiple times for the presence of metal in or on the body. Final screening occurs immediately prior to MRI scanning.

PROTOCOL TITLE: An MRI Study of Stress and Social Support

VERSION DATE: v.5.5 2022.09.20

There is no evidence for any long-term negative effect of MRI procedures on the body. The guidelines from the Bureau of Radiological Health (Food and Drug Administration) will be followed with regard to specific absorption rate (SAR) of energy (rf) and time-variant magnetic fields (dB/dt). All safety features of the clinically approved Siemens 3T scanner will be used to ensure that levels are well below the peripheral nerve stimulation threshold for both children and adults.

The MRI procedure involves exposure to a high level of noise while in the scanner environment. Participants are required to wear sound attenuating earplugs to protect their hearing. Beyond the risk to hearing, many participants find the scanner sounds annoying and monotonous. We provide additional headphones or foam padding over the top of the earplugs to further attenuate the background noise. This additional padding can become uncomfortable after long periods of time.

To reduce anticipatory stress for the scanner experience and to ensure that children feel comfortable with all MRI procedures, youth will complete a mock MRI scan in an MRI simulator. This pretend scanner has all of the primary features of the actual scanner, including an identically sized tunnel, the peripheral recording equipment, earplugs, headphones, video screen, audio system, button response box, and a speaker to play the scanner sounds around the tunnel, as if we were scanning, but with no magnetic field and no images produced.

Saliva Sampling. The saliva is collected on an absorbent swab. Any time anything is put in the mouth there is the risk of choking. This is a greater concern when participants are lying supine in the MRI environment. However, we deliberately use long sponge rolls that hang out of the mouth during saliva collection. The child is instructed to hold on to the end sticking out of the mouth while chewing on the other end until it is soggy. The age of participants, 11-14 years, also reduces the risk of choking as these youth are better able to follow experimenter instructions and to realize when they are placing the sponge too far into their mouths to be comfortable.

**13.1 Reproduction Risks:**

The risks of strong magnetic fields for the developing human fetus are unknown. To protect against these unknown but potential risks, we will screen all female youth who have started menstruating for possible pregnancy.

**13.2 Risks to Others: N/A**

**14.0 Potential Benefits to Participants**

*14.1 Potential Benefits:* This study confers no direct benefits to participants.

## 15.0 Statistical Considerations

*15.1 Data Analysis Plan:*

Preliminary Analyses to Determine Covariates Needed for Primary Analyses. The purpose of collecting data on potential covariates is to identify variables that are correlated with both the independent variable (social buffering condition, sex, pubertal stage) and the primary outcome measures. Those covariates that are associated with the independent and outcome variables will be controlled for in the primary analyses. Those that are not will be used to describe the sample, but will not need to be included in the analyses to obtain unbiased estimates. For each potential covariate, we will conduct correlations or t-tests with pubertal stage, and t-tests, ANOVAs, or chi-square tests (as appropriate) with sex and condition. If data do not confirm to modeling assumptions, we will use nonparametric analogs instead.

Preliminary Analyses of Imaging Data to Yield Primary Outcome Measures: fMRI data will be analyzed in FSL software (version 5.0.10) to generate voxel-wise contrast maps. Mean signal values will be extracted from these maps in a priori regions of interest for every participant using the methods described below. These preliminary analyses are used to generate the fMRI outcome variables of interest. The values of these outcome variables for each participant will be used in the general statistical analyses described in the next section. In total, these preliminary analyses will yield 6 primary task-related outcome variables, and 6 primary connectivity-related outcome variables.

Task-based analysis: Math under social evaluative stress In first level analyses (single subject, single-run), math performance will be modeled for each participant using a voxel-wise multiple regression analysis with a task predictor (math trials vs. blank trials), 24 regressors for head motion (Satterthwaite et al., 2013) and additional regressors to model censored data points (motion spikes). In subsequent analyses, we will explore the utility of including other time varying individual differences variables (e.g., heart rate, respiration) that are known to contribute to the BOLD signal. However, since these measures are expected to vary by stress condition, removing the effects of these physiological variables may unintentionally remove effects of interest. Particular care will be taken to reduce the confound of head motion by censoring (identifying as artifact) any data point with absolute motion greater than 2 mm (1 voxel) or a framewise displacement greater than 0.5 mm, as well as the immediately preceding and following data points. Data points with DVARS values exceeding the

individual's 75th percentile plus two times the interquartile range will also be censored. Participants with more than 25% of data points censored for artifact will be excluded from further analyses.

Second level analyses (single-subject, multiple runs) will test the within-subject contrast of math performed with judges (social evaluative stress) relative to math performed alone (without social evaluation) to identify brain regions differentially activated by social evaluative stress. Based on prior literature, we will examine activation in 5 *a priori* regions of interest, including "pain-related" brain regions (dorsal anterior cingulate [dACC], left and right anterior insula) and "safety-related" or regulatory brain regions (ventromedial prefrontal cortex [vmPFC], and left and right dorsolateral prefrontal cortex [dlPFC]). For each subject, the mean percent change in MR signal (averaged across voxels) between judged math and math alone will be extracted from each of these 6 regions. This analysis will generate the 6 task-related brain activation outcome variables (listed in section 4.3) for each participant.

Given that the MISTiC paradigm has not been used previously, it is possible that the most prominent regions of activity for this task may not match the *a priori* regions identified from the prior stress and social buffering literature. Therefore, we will also conduct an exploratory group-level analysis to identify primary regions of activation for the same socially evaluative math vs. non-evaluative math conditions (judged math vs. math alone, cluster corrected  $p < .005$ ). Because we expect that social buffering will alter the activity difference between social evaluative and non-evaluative math periods, we will use only the control condition (no social partner) to identify regions activated by this task. In the resultant group-level map, we will identify up to 4 primary regions of activation by selecting clusters that meet the cluster-corrected  $p < .005$  threshold, and then rank-ordering those regions by maximal z-statistic. Mean percent change in signal will be extracted for each participant (across all four buffering conditions) using anatomical masks derived from this analysis conducted in the control (no social partner) group. Therefore, exploratory analyses may generate up to 4 additional task-related MRI outcome variables.

Connectivity analysis: Speech preparation We are also interested in the neural correlates of anticipatory stress during the speech preparation period. However, the speech preparation period does not contain distinctive event markers needed for task-based fMRI analyses. Thus, to address the neural correlates of stress during speech preparation, we will use a seed-based connectivity approach to examine strength of functional connectivity between *a priori* seed regions of interest in the limbic system (amygdala, insula, hypothalamus) and target regions in the prefrontal

cortex (left and right vmPFC and dlPFC). To determine whether connectivity varies as a function of stress, we will compare connectivity during the speech preparation scan to connectivity during the baseline resting state scan. Preprocessing steps will include motion correction, unwarping, and eddy-current correction. An initial voxel-wise multiple regression analysis will be performed to remove effects of head motion (24 predictors), and estimates of CSF and white matter signals (2 predictors) from each subject's data. Initial analyses will not include a predictor for global signal given evidence that the inclusion of global signal may falsely introduce anticorrelations in the data (Murphy et al., 2009; Saad et al., 2012). However, in exploratory analyses, we will examine the degree to which the results change when global signal is included in the model.

First-level (single-subject, single run) connectivity analyses on the residualized data will include the time course for a seed region and predictors for censored data points. Two separate regression models will be run, one using the bilateral amygdala as the seed region, and the other seeding connectivity in the hypothalamus.

Second-level (single-subject, multiple-runs) analyses will test the within-subject contrast of connectivity during anticipatory stress (speech preparation) relative to baseline resting state for each seed-region. Masks of a priori target brain regions of interest will be applied to resultant contrast maps to extract stress-related connectivity in the bilateral vmPFC and left and right dlPFC for each individual. This analysis will generate the 6 connectivity-related brain outcome variables (2 seed regions x 3 target regions) for each participant. Because difference scores (speech preparation minus baseline) can mask the direction of connectivity effects (positive vs. negative correlations), follow-up simple-effects analyses will assess connectivity separately in the speech preparation and resting state periods, using the same a priori seed and target regions. These follow-up simple-effects analyses will allow us to interpret the directionality of connectivity effects.

15.2 Power Analysis: For the power analysis for the primary analyses, we calculated the minimum detectable effect size (MDES) assuming  $n = 200$ ,  $\alpha = .05$ , and power = .80 with 12 covariates in our model. Power was estimated in R (R Core Team) using the pwr library (Champely, 2018). A power analysis was performed to quantify the minimum detectable effect size ( $f^2$ ) for a three-way interaction between social buffering condition, sex, and pubertal stage within a multiple regression model controlling for the 12 covariates, all two-way interactions, and the main effects (the most complex model considered in our primary analysis, see Equation 1 below). Assuming these conditions, we should be able to detect an  $f^2$  of 0.056. In

other words, adding the three-way interaction to a model containing the covariates and all lower order interactions and main effects, the three-way interaction would need to explain an additional 5.6% of the variability to be detected. This falls between Cohen's criteria for a small ( $f^2 = .02$ ) and medium effect ( $f^2 = .15$ ) (Cohen, 1988). With a sample size of 200, even if we lose 40 of the participants to movement artifact for the imaging analyses, assuming all the previous conditions but a sample size of 160, we will still have an  $f^2$  of .070, or still within a small-medium effect size. As the number of covariates decreases, the size of the MDSE will decrease. Therefore, this represents a conservative estimate of the power for our primary analyses as we are likely to have fewer covariates in our models and will use multiple imputation to correct for missing data. For the two-way interaction and main effects models, described below, the power will be larger than these reported values as the models will be simpler.

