**Questionnaires.**

**Forms will be completed either on paper or online via Redcap.**

**Demographic Questionnaire:** Parents will complete information on pre-tax family income, education level of parent(s), composition of the household, and medications that the child regularly takes.

**Daily Diary:** The parent and the youth both will report the following for the child that day: the time of wake up, medication usage, illness/fever, physical activity, and caffeine consumption.

**Relationship Quality:** Participants will complete the Network of Relationships Inventory - Behavioral Systems Version (NRI-BSV, Furman & Buhrmester, 2009) for the parent who accompanies them and their close friend. This questionnaire is based on an integration of attachment and Sullivanian theory and assesses three systems that are expected to be key in close relationships: attachment, caregiving and affiliation. The scales are: companionship, seek safe haven, seek secure base, provide safe haven, provide secure base, conflict, antagonism and criticism. We will also add 3 scales from the NRI-Relationship Qualities Version: Emotional Support, Approval and Satisfaction. Each scale consists of 3 items scored on a 5-point Likert scale. Psychometric qualities are high. Condition differences in quality of relationships will be examined and included as covariates if groups differ significantly. Otherwise, in follow-up analyses we will examine whether social buffering effects are stronger in relationships the child views as more supportive.

**Four additional NRI scales (Seek Safe Haven, Seek Secure Base, Provide Safe Haven, Provide Secure Base) will be collected to better measure relationship quality. Completed participants will be contacted to complete these additional 12 questions and will be compensated for their time.**

**MacArthur Health and Behavior Questionnaire (HBQ) for 9-18 Year-Olds (Parent and Child, 2.1):** This questionnaire was developed by Marilyn Essex based on the original HBQ for 4-8 year olds. We have used it many

times. The scales we proposed to use here have high reliabilities (Cronbach alpha's > .8). We will use the peer scales (acceptance/rejection, bullied, relational victimization, asocial, behavioral inhibition) and broad-band symptoms scales (Internalizing, Externalizing). These measures will be examined for balance across groups and if differences by condition, pubertal stage, or sex are found, will be entered as covariates.

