### **Physiological Measures.**

**Stress Hormones:** We will assay saliva samples for stress sensitive hormones: cortisol and alpha-amylase. Saliva will be collected using SalivaBio Oral Swabs (SOS) or passive drool and stored frozen at -20°C until shipped for assay. All testing will be conducted in the late afternoon to control for circadian rhythm. Medications will be recorded from parent report and classes of drug codes will be used to group meds by presumed mechanisms of action and will be entered as covariates (Granger et al., 2009). Systemic glucocorticoid medications are an exclusion criterion. For each analyte, we will calculate area under the curve from intercept (AUCi) to provide a single measure for the main analysis.

**Pubertal Hormones - DHEA, Testosterone, Estradiol:** Sufficient saliva will be obtained at sampling to assay for these additional pubertal hormones. These assays will be performed if we obtain a sex by condition by pubertal development (3-way) interaction on key outcome measures. If so, these measures may provide insight into the mechanism of these interactions ([Butler et al., 1989](#); [Mehta, Mor, Yap, & Prasad, 2015](#)).

**Physiological Recording:** Participants will wear standard Siemens physiological recording equipment for the MRI environment (respiration belt, and pulse oximeter or EKG leads). Samples will be collected throughout the entire MRI scan. Response measures will be computed by regressing the stress condition values on comparison condition values and saving the residual as the response measure.

All questionnaires and surveys are included in the ETHOS portal. Contact information and child age will be obtained from an existing registry of families who have expressed interest in child development research (specifically, parent name(s), address, phone number, email address, child

**PROTOCOL TITLE:** An MRI Study of Stress and Social Support

**VERSION DATE:** v.5.5 2022.09.20

name, child sex, and child birthdate). All other data will be acquired directly from the participants, and information obtained from the participant registry will be verified verbally with the parent.

**5.3 Study Duration:** Participants will attend two sessions. Each session will last approximately 2 hours.

- All participants will be enrolled and assessed within a 30-month period.
- Primary data analysis endpoints will be available within 1 year of the end of data collection (i.e., 42 months from initial enrollment).

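### Sections 15.1 and 5.2 give different covariate entry rules with no order of precedence, and the 15.1 screen usually drops a purely prognostic covariate, at a precision cost the documents do not fix

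*Combined protocol and SAP*

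**What the plan says.** Section 15.1 sets a two-part test for all candidate covariates. A variable must be associated with a design factor (condition, sex or pubertal stage) and with the outcome: "Those covariates that are associated with the independent and outcome variables will be controlled for in the primary analyses". The others describe the sample "but will not need to be included in the analyses to obtain unbiased estimates". The tests listed are against puberty, sex and condition. No test against the outcome and no screening level is given.

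Section 5.2 has separate rules:
- HBQ scales are checked for balance and, "if differences by condition, pubertal stage, or sex are found, will be entered as covariates".
- For the relationship-quality inventory (NRI): "Condition differences in quality of relationships will be examined and included as covariates if groups differ significantly". The next sentence makes a further analysis depend on that test: "Otherwise, in follow-up analyses we will examine whether social buffering effects are stronger in relationships the child views as more supportive".
- In the stress-hormone paragraph, for medications, "classes of drug codes will be used to group meds by presumed mechanisms of action and will be entered as covariates".

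The test-day diary records "the time of wake up, medication usage, illness/fever, physical activity, and caffeine consumption", with no covariate rule of its own. Section 15.2 allows for 12 covariates, unnamed in the supplied text, and expects fewer. Section 15.3 steps from the three-way interaction to two-way interactions to main effects. Its mediation model takes its covariates from the preliminary screen.

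**The concern.** There are two problems.

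First, the rules disagree about the same variables, and the choice between them would be made with outcome associations in view. The mediation model takes only what the preliminary screen selects. Medication classes could therefore adjust the cortisol regression and be absent from the mediation model for that same cortisol outcome.

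Second, Section 15.1 justifies leaving variables out on grounds of bias alone. For a randomised comparison that is correct but incomplete. A variable balanced across conditions that predicts the outcome reduces residual variance, and the rule tends to exclude exactly that kind of variable. What is at stake is reproducibility of the adjusted model, plus some power for the condition effects and their interactions.

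**Working it through.** **1. The rules side by side**

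| Variable | Section 15.1 | Section 5.2 |
|---|---|---|
| HBQ scale that differs by sex, unrelated to outcome | out | in |
| NRI scale related to puberty and outcome, balanced by condition | in | out |
| Medication class that fails the screen, hormone outcome | out | in |

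The first row need not be rare. Section 5.2 names seven HBQ scales (five peer, two symptom), each tested against three factors, so 21 tests. At an assumed 5% each, and if independent, the chance of at least one false flag is 1 − .95^21 = .66. Correlated scales would make it lower.

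**2. The plan's own power figure**

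Section 15.2 states a detectable f² of .056 at n = 200 and .070 at n = 160 (alpha .05, power .80, 12 covariates). For the three-way term with three conditions, u = 2. The model has 12 design parameters and 12 covariates, so v = 200 − 24 = 176, or 160 − 24 = 136. With noncentral F and λ = f²(u + v + 1), the detectable f² is .0548 and .0709. Power at the stated values is .809 and .795. The figures reproduce closely. With no covariates (v = 188) the detectable f² is .051.

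**3. How often a purely prognostic covariate is dropped**

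The documents give no screening level, so 5% is assumed. The chance that an unrelated variable is flagged against at least one of three factors is 1 − .95³ = .143, so it fails that half of the rule about 86% of the time. Adding the outcome half, simulation (10,000 runs, n = 200 in arms of 67/67/66, parent effect 0.5 SD) gives:

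| Covariate-outcome r (assumed) | .1 | .2 | .3 | .5 |
|---|---|---|---|---|
| Dropped, 5% screen | 96% | 88% | 86% | 86% |
| Dropped, 10% screen | 90% | 76% | 73% | 73% |

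The covariate must be unrelated to all three factors. If it correlates .1 or .2 with puberty, the chance of no design-factor flag at 5% falls from 86% to about 64% or 17%.

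**4. What dropping it costs**

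Power in per cent, 5% rule versus always adjusting:

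| Test | r = .1 | .2 | .3 | .5 |
|---|---|---|---|---|
| Tukey pairwise, 0.5 SD | 69.2 v 69.6 | 68.8 v 70.5 | 69.9 v 73.6 | 71.7 v 82.4 |
| Pairwise without Tukey | 81.6 v 81.7 | 81.5 v 82.7 | 82.5 v 85.0 | 83.3 v 91.1 |
| Condition by puberty, slope difference 0.5 | 83.8 v 83.9 | 83.7 v 85.1 | 83.9 v 86.3 | 84.4 v 92.0 |

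For the three-way term, take f² = .056 as the unadjusted effect (power .809). The adjusted effect is .056/(1 − r²), and power under the rule is .857 × unadjusted + .143 × adjusted.
- r = .3: f² = .0615, adjusted power .847; rule .857 × .809 + .143 × .847 = .815.
- r = .5: f² = .0747, adjusted power .911; rule .857 × .809 + .143 × .911 = .824.

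Across the tests the gap is about 0 to 2 points at r of .2 or below, 2 to 4 at .3 and 8 to 11 at .5. Benjamini-Hochberg correction is not modelled.

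**5. Validity of the condition tests**

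Type I error under the 5% rule at r of .2 to .5 is 4.6 to 4.8% pairwise and 4.8 to 5.0% for the condition-by-puberty test. Adjusting for a useless covariate (r = 0) costs 0.2 points or less.

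**The case against.** The Section 5.2 rules can be read as exceptions for named instruments, with Section 15.1 as the general rule. That reading is coherent, but no section states it, Section 15.1 has no carve-out, and the mediation model draws on the preliminary screen only.

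The medication rule sits in the hormone paragraph. A reader might infer that it governs every regression in Section 15.3. The documents do not plainly extend it to the imaging or heart-rate models, and where it does apply the discard calculation is beside the point.

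The precision cost rests on assumed inputs: effect size, slope difference, screening level and r. No document variable is shown to reach r = .5. Late-afternoon testing and the medication exclusions already remove part of what wake time and medication could explain. Section 15.1's wording on omission is also permissive, although no other general route into the model is given. All this stands and limits the claim on size.

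The screens also serve a purpose. Sex and puberty are not randomised, and HBQ scales may confound them. A short set of prognostic variables alone would lose that protection, so the fix has to keep it.

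**Conclusion.** The concern holds as a conflict of rules plus a modest, uncertain loss of precision. The conflict does not depend on any assumed number. The loss does: it is 4 power points or less unless a covariate correlates near .5 with outcome, and the documents do not show how strong any covariate is.

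Three stronger readings are not supported. A reader might infer biased condition effects or inflated type I error, but randomisation protects the contrasts and the simulated error rates are at or just below 5%. That simulation uses one covariate under one rule; it does not model choosing among rules, and it says nothing about bias in the sex and puberty effects. A reader might infer that the power calculation is wrong, but it reproduces. A reader might infer that the cortisol analysis wrongly omits a baseline value, since "we will calculate area under the curve from intercept (AUCi) to provide a single measure for the main analysis". The supplied text does not say whether the first saliva sample precedes partner exposure and the stressor. It also contains neither Equation 1 nor the list of 12 covariates, so baseline adjustment cannot be judged and forms no part of this point.

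**What to change.** Before analysis, name one covariate set for each outcome. Use it at every step of the Section 15.3 regressions and in the mediation model, whatever the significance tests show. Each set should hold:
- expected prognostic variables already collected and unaffected by partner assignment: selected test-day diary items, and medication classes at least for the hormone outcomes. NRI items that completed participants answer afterwards do not qualify;
- named confounders of the sex and pubertal-stage effects, such as age (Section 8.3 already treats it as confounded with puberty) and those HBQ scales judged in advance to be confounders.

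Keep within the 12 covariates of Section 15.2. State that the set replaces the entry rules in Section 15.1 and in the Section 5.2 questionnaire text, and that the relationship-quality follow-up no longer depends on a balance test.

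The cost is wording and about one degree of freedom per covariate. The detectable f² for the three-way term moves from .051 with no covariates to .055 with 12. Where a covariate such as age correlates with puberty, the interval for the pubertal-stage main effect will widen somewhat; that amount has not been calculated. No new data are needed.
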